1 CLINICAL STUDY SYNOPSIS

STUDY TITLE	Utilizing Novel Dipole Density Capabilities to Objectively Visualize the Etiology of Recurrent Atrial Fibrillation Following a Failed AF Ablation (RECOVER AF)
DEVICE NAME	AcQMap® High Resolution Imaging and Mapping System
DEVICE SHORT NAME	AcQMap
DEVICE COMPONENTS	
The AcQMap System consists of the following components:
 
• The AcQMap 3D Imaging and Mapping Catheter (AcQMap Catheter)• The AcQGuide® Steerable Delivery Sheath• The AcQMap Console• The AcQMap Workstation• The AcQMap Patient Electrode Kit
INDICATION FOR USE (INTENDED USE)	The AcQMap Imaging and Mapping System is intended to be used in the right and/or left atria to visualize the selected chamber and display atrial electrical impulses.
SPONSOR	Acutus Medical®, Inc. [name] [name]
STUDY OBJECTIVES	To evaluate the performance and efficiency of the AcQMap Imaging and Mapping System in an ablation retreatment procedure for recurrent atrial fibrillation following a failed AF ablation
STUDY DESIGN	A prospective, single-arm, multi-center, multi-national, non-randomized, post-market study designed to provide clinical data regarding the use of the AcQMap High Resolution Imaging and Mapping System during an atrial fibrillation retreatment ablation procedure. The patient population includes men and women, eighteen (18) years of age or older, who in the past twenty-four (24) months have had no more than two (2) previous left-atrial ablations for AF treatment. The treatment plan must include evaluation and ablation (as indicated) of pulmonary vein reconnections plus AcQMap guided non-PV substrate ablation. Subject assessments will occur at screening, procedure, hospital discharge, 3-, 6-, and 12-months.
SAMPLE SIZE	Enrollment of up to one hundred (100) subjects that complete the ablation procedure using the AcQMap System
CLINICAL SITES	Up to fifteen (15) Clinical Sites
DURATION	Enrollment is anticipated to take approximately twelve (12) months. Post-procedure assessments will occur at 3-, 6-, and 12-months. The

	
total study duration is anticipated to be approximately twenty-four (24) months.

OUTCOME MEASURES	
The measurable objectives are a descriptive analysis of the following:
 
 • At the procedure conclusion, confirmation of electrical isolation of all pulmonary veins and elimination/modification of all non-PV targets as identified by the AcQMap System • Recording of all subjects who are atrial fibrillation free from events lasting > 30 seconds at 6-, and 12-months as measured by a 48-hour continuous ECG 
 ○ A subset analysis of AAD use ○ A subset analysis of subjects with freedom from AF/AT/AFL events lasting > 30 seconds as measured by a 48-hour continuous ECG • Documentation of procedure data including total time, fluoroscopy time, ablation times for PVI, and ablation times for non-PV targets • Safety – Recording of all device and procedure related safety events through 24 hours post-ablation
INCLUSION CRITERIA	
The patient population will consist of men and women eighteen (18) years of age or older, scheduled for a repeat endocardial ablation of AF following a failed ablation for atrial fibrillation.
 
A potential subject will be eligible for study enrollment only if all the following inclusion and none of the exclusion criteria apply:
 
IC 1 Male or female eighteen (18) years of age or older IC 2 Currently scheduled for a repeat endocardial ablation of AF IC 3 Willingness, ability, and commitment to participate in baseline and follow-up evaluations for the full length of the study IC 4 Willingness and ability to give informed consent

EXCLUSION CRITERIA	
EC 1 In the opinion of the Investigator, any known contraindication to a left-atrial ablation or concerns for left-atrial thrombus EC 2 No more than two (2) previous left-atrial ablations EC 3 Atrial arrhythmias secondary to electrolyte imbalance, thyroid disease, or any other reversible or non-cardiac cause EC 4 Structural heart disease or implanted devices as described below:
 
 a. An implanted pacemaker or ICD b. Previous cardiac surgery, ventriculotomy, or atriotomy (excluding atriotomy for CABG) c. Previous cardiac valvular surgical or percutaneous procedure, or prosthetic valve d. Interatrial baffle, closure device, patch, or PFO occluder e. Presence of a left atrial appendage occlusion device f. Unstable angina or ongoing myocardial ischemia

	
EC 5 History of blood clotting or bleeding disease
 
EC 6 Pregnant or lactating (current or anticipated during study follow up)
 
EC 7 Current enrollment in any study protocol sponsored by Acutus Medical or any other study that may impact the results of RECOVER AF
 
EC 8 Any other condition that, in the judgment of the investigator, makes the patient a poor candidate for this procedure, the study, or compliance with the protocol (includes vulnerable patient population, mental illness, addictive disease, terminal illness with a life expectancy of less than two years, extensive travel away from the research center, etc.)

DATA COLLECTION	
 • Screening data to include demographics, arrhythmia history, current AAD use, and previous AF ablation history (3D system use, ablation targets including PV and non-PV locations, etc.). • Procedure data to include procedure time, fluoroscopy time, maps of ablation targets, pre-and post-procedure rhythm, DCCV for conversion, and a post-ablation AcQMap in the procedure ending rhythm. All alterations to ablation due to esophageal proximity will be noted. • Follow-up data to include safety events reported through discharge, continuous ECG monitor (≥ 48-hr), and AAD medications at 3-, 6- and 12-months post-procedure.
STATISTICAL METHODS AND ANALYSIS SUMMARY	Descriptive statistical analysis of all data recorded
FOLLOW-UP EVALUATIONS	See Table Below

Table 1: Schedule of Events

	Screening & Baseline	Procedure	Discharge	3-month (± 14 days)	6-month (± 30 days)	12-Month (± 30 days)	Retreatment Visit (if medically necessary)
CIP Informed Consent	X						
Medical History	X						
Arrhythmia Management Assessment				X	X	X	X
Cardiovascular Exam	X		X				X
AAD Medications	X	X	X	X	X	X	X
Procedure Data		X					X
Adverse Events		X	X				X
12-lead ECG		X	X	X	X	X	X
Continuous 48-hr ECG monitor				X	X	X	X (prior to retreatment)

4 ABBREVIATIONS

3D	Three Dimensional
AAD	Anti-Arrhythmic Drug
ACT	Activated Clotting Time
ADE	Adverse Device Effect
AE	Adverse Event
AF	Atrial Fibrillation
AFL	Atrial Flutter
AIU/PIU	Ablation Interface Unit/Patient Interface Unit
AT	Atrial Tachycardia
ATP	Adenosine
CABG	Coronary Artery Bypass Grafting
CIP	Clinical Investigational Plan
CMP	Clinical Monitoring Plan
CPM	Clinical Project Manager
CRA	Clinical (or Contract) Research Associate
CRO	Contract Research Organization
CRF	Case Report Form
CTI	Cavo-tricuspid Isthmus
DCCV	Direct Current Cardioversion
DMP	Data Management Plan
EC	Ethics Committee
eCRF	Electronic Case Report Form
ECG	Electrocardiogram
EDC	Electronic Data Capture
EGM	Electrogram
FDA	Food and Drug Administration
GCP	Good Clinical Practices
ICF	Informed Consent Form
ICH	International Conference on Harmonisation
IA	Investigator Agreement
ICD	Implantable Cardioverter Defibrillator
IFU	Instructions For Use
ISF	Investigator Site Files
ISO	International Organization for Standardization
IV	Intravenous
LA	Left Atrium
LFU	Lost to Follow-Up
OM	Operator's Manual

PAF	Paroxysmal Atrial Fibrillation
PFO	Patent Foramen Ovale
PI	Principal Investigator
PV	Pulmonary Vein
PVI	Pulmonary Vein Isolation
QAP	Quality Assurance Procedure
RF	Radio Frequency
RMV	Routine Monitoring Visit
SADE	Serious Adverse Device Effect
SAE	Serious Adverse Event
SIV	Site Initiation Visit
SOC	Standard of Care
SOP	Standard Operating Procedure
SVT	Supraventricular Tachycardia
SQV	Site Qualification Visit
TIA	Transient Ischemic Attack
TMF	Trial Master File
TS	Transseptal Puncture
UADE	Unanticipated Adverse Device Effect
USFDA	United States Food and Drug Administration
WACA	Wide Area Circumferential Ablation

5 INTRODUCTION TO THE CLINICAL INVESTIGATIONAL PLAN/PROTOCOL

5.1 Background

Atrial fibrillation (AF) is among the most prevalent arrhythmias in the world today affecting approximately 1.5-2% of the general population. The age of patients with AF is steadily rising and now averages between 75 and 85 years of age. AF is associated with a five-fold risk of stroke, a three-fold incidence of congestive heart failure, and higher mortality.¹

Symptoms arise from the rapid, irregular rhythm as well as the loss of cardiac pump function related to uncoordinated atrial contractions. These uncoordinated contractions also allow blood to pool in the atria and may ultimately lead to thromboembolism and stroke.

AF is characterized by a chaotic contraction of the atrium in which an electrocardiogram (ECG) recording is necessary to diagnose the arrhythmia. Any arrhythmia that has the ECG characteristics of AF and lasts sufficiently long for a 12-lead ECG to be recorded, or at least 30 seconds on a rhythm strip, should be considered an AF episode.^{2,3}

The diagnosis requires an ECG or rhythm strip demonstrating: (1) Irregular RR intervals (in the absence of complete AV block), (2) no distinct P waves on the surface ECG, and (3) an atrial cycle length (when visible) that is usually variable and less than 200 milliseconds.³

AF can be characterized into four classifications:

- Paroxysmal AF (PAF) is defined as AF that terminates spontaneously or with intervention within seven days of onset.

¹ Camm AJ, et al. 2012 focused update of the ESC Guidelines for the management of atrial fibrillation: an update of the 2010 ESC Guidelines for the management of atrial fibrillation--developed with the special contribution of the European Heart Rhythm Association. *Europace*, 2012 Oct; 14(10):1385-413

² Calkins H, Brugada J, Packer DL et al. HRS/EHRA/ECAS expert Consensus Statement on catheter and surgical ablation of atrial fibrillation: recommendations for personnel, policy, procedures and follow-up. A report of the Heart Rhythm Society (HRS) Task Force on catheter and surgical ablation of atrial fibrillation. *Heart Rhythm*. Jun 2007;4(6):816–861

³ Camm AJ, Kirchhof P, Lip GY et al. Guidelines for the management of atrial fibrillation: the Task Force for the Management of Atrial Fibrillation of the European Society of Cardiology (ESC). *Eur Heart J*. Oct 2010;31(19):2369–2429

5.2 Clinical Study Design Justification

Previous clinical studies utilizing the AcQMap System in an ablation procedure for supraventricular tachycardias (SVTs) have initially demonstrated an acceptable safety profile when mapping and imaging cardiac chambers. The RECOVER AF study is a prospective, single-arm, multi-center, multi-national, non-randomized, post-market study designed to provide clinical data regarding the use of the AcQMap High Resolution Imaging and Mapping System during an atrial fibrillation retreatment ablation procedure. Recording of all Serious Adverse Events/Device Effects occurring during the first twenty-four (24) hours post-procedure will be used to assess the safety related to the AcQMap Catheter, AcQGuide Steerable Sheath, and the AcQMap System.

Since it is hypothesized the technology advances of dipole density mapping may better identify and more precisely direct lesion locations during atrial arrhythmia ablations, the study is additionally designed to record longer term (6- and 12-month) data on the effectiveness of the ablation procedure in the treatment of the arrhythmia. An analysis of treatment success (defined as freedom from atrial arrhythmias at 6- and 12-months), compared to literature based historical controls, may offer insight regarding the ability of the AcQMap System to effectively and accurately identify appropriate ablation targets.

Automatic, instantaneous, and simultaneous 3D display of the LA surface with associated charge densities may potentially shorten atrial arrhythmia ablation procedure time and provide an intuitive tool to rapidly identify and guide effective treatment.

5.3 Indication for Use Statement

The AcQMap Imaging and Mapping System is intended to be used in the right and/or left atria to visualize the selected chamber and display atrial electrical impulses.

5.4 Device Description

5.4.1 General System Description

The AcQMap System is designed to create a 3D image of a heart chamber's endocardial surface in which catheters can be navigated and a chamber-wide electrical activation map can be overlaid for percutaneous procedures. The AcQMap System should only be used by physicians thoroughly trained in electrophysiology procedures and trained on the use of the AcQMap System.

AcQMap System Hardware

The AcQMap System hardware consists of the AcQMap Console, AcQMap Workstation and the AcQMap Ablation Interface Unit/Patient Interface Unit (AIU/PIU). The AcQMap Console contains all electronics for interfacing with patient-contacting devices such as the AcQMap Catheter and the Patient Electrode Kit.

5.4.2 The AcQMap 3D Imaging and Mapping Catheter

The AcQMap 3D Imaging and Mapping Catheter is a diagnostic, sterile, single-use device that has a polymeric catheter torque shaft, an integral handle and a flexible, metallic deployable/retractable array.

5.4.3 AcQGuide Steerable Sheath

The AcQGuide Steerable Sheath is a single-use, sterile, delivery sheath consisting of a deflectable shaft with a lumen, integral handle with steering mechanism, hemostasis valve and flush port. The sheath is compatible with other Acutus Medical catheter products. The sheath can be placed within the desired heart chamber thus allowing the AcQMap Catheter to be introduced, deployed, and directed within the chamber as needed.

6 CLINICAL STUDY

6.1 Clinical Study Objective

The objective of the clinical study is to evaluate the performance and efficiency of the AcQMap Imaging and Mapping System in an ablation retreatment procedure for recurrent atrial fibrillation following a failed AF ablation.

6.2 Clinical Study Design

The clinical study is a prospective, single-arm, multi-center, multi-national, non-randomized, post-market study designed to provide clinical data regarding the use of the AcQMap High Resolution Imaging and Mapping System during an AF retreatment ablation procedure. The patient population includes men and women, eighteen (18) years of age or older, who in the past twenty-four (24) months have had no more than two (2) previous LA ablations for AF treatment. Subject assessments will occur at screening, procedure, hospital discharge, 3-, 6-, and 12-months.

6.2.1 Measurable Objective

The measurable objectives are a descriptive analysis of the following:

- At the procedure conclusion, confirmation of electrical isolation of all pulmonary veins and elimination/modification of all non-PV targets as identified by the AcQMap System

- Recording of all subjects who are atrial fibrillation free from events lasting > 30 seconds at 6- and 12-months as measured by a 48-hour continuous ECG
 - A subset analysis of AAD use
 - A subset analysis of subjects with freedom from AF/AT/AFL events lasting > 30 seconds as measured by a 48-hour continuous ECG
- Documentation of procedure data including total time, fluoroscopy time, ablation times for PVI, and ablation times for non-PV targets
- Safety - Recording of all device and procedure related safety events through twenty-four (24) hours post-ablation

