6.4 Clinical Study Sample Size and Clinical Sites

Up to one hundred (100) patients will be treated at up to fifteen (15) clinical sites in Europe. The sample size will include only those that complete an ablation procedure using the AcQMap technology (Treatment Subjects).

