6.5 Clinical Study Enrollment Definitions

For the purposes of this clinical study, the following definitions regarding the status of a subject will apply:

Pre-Treatment Subject – Any subject who has signed an informed consent form, is deemed study eligible by meeting all of the inclusion and none of the exclusion criteria, and who has the venous access portion of the ablation procedure initiated. Pre-Treatment subjects that do not complete the AcQMap procedure will be followed for adverse events through hospital discharge. In addition to the discharge eCRF, a study completion eCRF will be completed. No follow-up beyond the hospital discharge will be required.

Treatment Subject – Any pre-treatment subject who completes the ablation procedure using the AcQMap System. A completed ablation procedure is defined as a procedure where the PVI was evaluated and additional non-PV targets were mapped and ablated using the AcQMap System. Treatment subjects should be followed for all study outcome measures for the full duration of the clinical study.

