7.2.2 Procedure Data Collection

Collection of data generated during the procedure should include:

- Recording of 12-lead ECG at procedure start
- Recording of 12-lead ECG for predominant atrial arrhythmia(s)
- Recording of 12-lead ECG at procedure completion
- Total procedure time (from first venous access to last cardiac catheter removed)
- Total ablation time for PVI and non-PVI ablations
- Total fluoroscopy time for the ablation procedure
- Recording of all DCCV used during the procedure
- Recording of all IV cardiac medications infused during the procedure
- All alterations to ablation strategies due to esophageal proximity

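### The first outcome pools elimination with an undefined modification of non-PV targets and is followed only in subjects whose targets were ablated with AcQMap; vein isolation is in neither procedure data list

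*Combined protocol and SAP*

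**What the plan says.** The first of four descriptive measures in section 6.2.1, repeated in the synopsis, is confirmation at the end of the procedure that all pulmonary veins are isolated, together with "elimination/modification of all non-PV targets as identified by the AcQMap System". Neither elimination nor modification is defined anywhere, and no threshold is set.

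Section 6.4 counts only Treatment Subjects, up to 100, towards the sample. Section 6.5 defines their completed procedure as one where "the PVI was evaluated and additional non-PV targets were mapped and ablated using the AcQMap System", and follows them for all outcome measures. For the others it says: "Pre-Treatment subjects that do not complete the AcQMap procedure will be followed for adverse events through hospital discharge". They also get a study completion form, and nothing after discharge is required.

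Two places list procedure data:
- Section 7.2.2 opens with "Collection of data generated during the procedure should include" and names ECGs, procedure, ablation and fluoroscopy times, cardioversions, intravenous cardiac drugs, and changes of strategy because of the esophagus.
- The synopsis also names maps of the ablation targets and "a post-ablation AcQMap in the procedure ending rhythm".

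Section 7.2.1 puts PVI strategy and catheter type on the procedure eCRF. Section 8 promises descriptive statistics, with no hypothesis and no power calculation.

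**The concern.** The stated objective (section 6.1) is to evaluate the system's performance and efficiency. Section 5.2 hopes to learn whether AcQMap identifies the right ablation targets. The first outcome is the measure closest to that question at the time of the procedure, and three features weaken it.

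- **Numerator.** A target that was altered counts the same as one that was abolished, and no rule separates the two. Sites could score the same result differently, and a reader of the pooled figure cannot recover the split.
- **Denominator.** A subject whose map could not be made, or whose non-PV targets were not ablated with AcQMap, does not become a Treatment Subject. Those procedures say most about performance, and they leave the figure.
- **Data source.** The vein component is not tied to any listed data item. The target component rests on maps that only one of the two lists mentions.

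At stake is a percentage that reads as device performance but describes a favourably selected group. Section 13.2 foresees both publication and support for a regulatory filing.

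**Working it through.** The plan gives no rate, margin or threshold for this outcome, so there is no figure to reproduce. The check compares the text and then illustrates the denominator.

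**1. Selection against outcome**

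| Component | Needed to be a Treatment Subject (6.5) | Needed to meet the outcome (6.2.1) |
|---|---|---|
| Pulmonary veins | PVI evaluated | All veins isolated |
| Non-PV targets | Targets mapped and ablated with AcQMap; not stated to be all of them | All identified targets eliminated or modified |

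Selection brings subjects close to meeting the non-PV requirement without guaranteeing it. It does not build in vein isolation.

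**2. Outcome against listed data**

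| Item needed | Section 7.2.2 | Synopsis | Section 7.2.1 |
|---|---|---|---|
| Vein isolation at procedure end | No | No | No (strategy and catheter type only) |
| Target maps | No | Yes | No |
| Post-ablation map | No | Yes | No |
| Final status of each target | No | No | No |

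The synopsis maps bear on target status, but no rule turns a map into eliminated, modified or untreated.

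**3. Effect of the denominator.** Assume 100 Treatment Subjects (the plan's maximum), all meeting the outcome, and k further Pre-Treatment Subjects who do not complete and are counted as not met. The plan gives no value for k; 5, 10 and 20 are assumptions. Rate = 100/(100 + k), with exact (Clopper-Pearson) 95% intervals:

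| k | Rate | 95% interval | Change from 100% |
|---|---|---|---|
| 0 | 100/100 = 100% | 96.4 to 100% | – |
| 5 | 100/105 = 95.2% | 89.2 to 98.4% | −4.8 points |
| 10 | 100/110 = 90.9% | 83.9 to 95.6% | −9.1 points |
| 20 | 100/120 = 83.3% | 75.4 to 89.5% | −16.7 points |

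If fewer completers meet the outcome, their rate is multiplied by the same factor, 100/(100 + k).

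**4. How far selection can carry the whole outcome.** Take the extreme case in which the non-PV component is met in every Treatment Subject. The combined rate then equals the vein isolation rate v, and the chance that all 100 subjects meet the outcome is v^100. For assumed v of 0.90, 0.95 and 0.99 this is below 0.01%, 0.6% and 37%. So even in that case the vein component can pull the combined figure below 100%.

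**The case against.** A reader might infer that the outcome can hardly fail, or that it will be near 100% by construction. The documents do not support that. The outcome needs both components. Section 6.5 asks only that PVI was evaluated, so isolation can fail. A target can also be left untreated: section 6.5 does not say that all targets were ablated, and section 7.2.2 foresees changes of strategy near the esophagus. Step 4 of the working bears this out.

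Two further inferences also go too far. An undefined modification is not one that any lesion would satisfy. And the plan says that AcQMap identifies the targets, but not what judges the result.

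The defence can add that the section 7.2.2 list is introduced with *should* and is not complete: section 7.2.1 puts items on the eCRF that 7.2.2 omits. The eCRF is not in the documents, so vein status may be collected after all. The study is descriptive, this measure is one of four and is not designated primary, and section 5.2 defines treatment success by rhythm at 6 and 12 months.

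These points limit the claim but do not remove it. Silence in the lists does not prove that vein status goes unrecorded, yet the plan gives this outcome no named source. Section 7.2.2 does list the times needed for the third measure. A descriptive percentage still needs a defined numerator and a denominator that is not selected on part of the result. The selection rule is explicit in sections 6.4 and 6.5.

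**Conclusion.** The concern holds in limited form. The non-PV component pools two different results without defining either, and it is followed in a group selected for having had non-PV targets ablated with AcQMap. Incomplete AcQMap procedures therefore leave the performance figure. The vein component is not favoured in this way, but its status at procedure end is in neither data list, and section 7.2.2 omits the maps that the synopsis names.

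Under the assumed 5 to 20 non-completers, the restriction is worth about 5 to 17 percentage points if every completer meets the outcome. The true size depends on how many Pre-Treatment Subjects do not complete, which the plan does not predict. Section 8 names no analysis set, so the denominator is read from sections 6.4 and 6.5. The effect of pooling cannot be sized from the documents, because they give no elimination or modification rates.

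**What to change.** In section 6.2.1 and the synopsis, replace the single measure with three, reported separately:
- (a) subjects with all veins isolated at procedure end;
- (b) subjects with all non-PV targets eliminated, and the proportion of targets eliminated;
- (c) targets modified only, and targets left untreated.

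Define elimination and modification in advance against the post-ablation map that the synopsis already lists. That map is itself an AcQMap product, so the report should say so.

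Report these over all Pre-Treatment Subjects, with incomplete AcQMap procedures counted as not met, beside the Treatment Subject figure. Tabulate the reasons for non-completion so that a reader can separate mapping failures from other causes.

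In section 7.2.2, add the isolation status of each vein at procedure end and the final status of each target, and reconcile the list with the synopsis so that both name the target maps and the post-ablation map.

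The cost is a small vein-and-target table on the procedure eCRF, a few more minutes of data entry, and a less favourable acute figure. The change concerns recording and reporting only.

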7.3.2 Visits at Three, Six and Twelve Months

The following evaluations will be performed during each clinic follow-up visit. Data will be recorded on the Follow-Up eCRFs.

- Arrhythmia recurrence/treatment since last visit
- AAD use and changes since last visit
- DCCV history since last visit
- 12-lead electrocardiogram
- 48-hour continuous monitor (may include Holter recording, BardyDx CAM or equivalent)

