7.4 Recurrence of Atrial Fibrillation/Atrial Flutter/Atrial Tachycardia

Occurrences of symptomatic AF or other tachyarrhythmias during the first 90 days post-ablation (blanking period) may be transient in nature and not associated with the long-term effectiveness of the ablation treatment. However, prolonged AF should be treated as soon as possible to maintain SR during the remodeling period. Treatment should follow the Investigator's SOC for arrhythmia recurrence, which may include a DCCV and/or AAD administration. If the Investigator elects to repeat an ablation, a 48-hour continuous ECG monitor will be worn within two weeks and no later than 3 days prior to the procedure to document the presenting rhythm. The AcQMap System will be used during the procedure. Procedure and discharge data will be collected as part of RECOVER AF. There will be no adjustments to the scheduled follow-up periods and the study will be completed at 12-months post RECOVER AF index procedure.

Table 2: Schedule of Events

	Screening & Baseline	Procedure	Discharge	3-month (± 14 days)	6-month (± 30 days)	12-Month (± 30 days)	Retreatment Visit (if medically necessary)
CIP Informed Consent	X						
Medical History	X						
Arrhythmia Management Assessment				X	X	X	X
Cardiovascular Exam	X		X				X
AAD Medications	X	X	X	X	X	X	X
Procedure Data		X					X
Adverse Events		X	X				X
12-lead ECG		X	X	X	X	X	X
Continuous 48-hr ECG monitor				X	X	X	X (prior to retreatment)

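### AF-free status rests only on the 48-hour recordings at months 6 and 12; no rule brings in documented interim recurrence, cardioversion or repeat ablation, and no measure of freedom from recurrence after the index procedure is defined

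*Combined protocol and SAP*

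**What the plan says.** Section 6.2.1, and the Outcome Measures row of the synopsis, record the subjects who are "atrial fibrillation free from events lasting > 30 seconds at 6- and 12-months as measured by a 48-hour continuous ECG". The wider rhythm analysis uses the same instrument: "A subset analysis of subjects with freedom from AF/AT/AFL events lasting > 30 seconds as measured by a 48-hour continuous ECG". Section 5.2 describes treatment success as being free of atrial arrhythmias at those two visits. It adds that a comparison with historical controls from the literature may show whether the system finds the right ablation targets.

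The protocol collects more than these recordings:

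- Section 7.3.2 lists "Arrhythmia recurrence/treatment since last visit", "DCCV history since last visit" and a 12-lead ECG at months 3, 6 and 12.
- Section 7.4 says that, before a repeat ablation, "a 48-hour continuous ECG monitor will be worn within two weeks and no later than 3 days prior to the procedure". It continues: "The AcQMap System will be used during the procedure". Procedure and discharge data are then collected, and the visit schedule stays tied to the index procedure.
- Section 7.4 also names a blanking period: recurrences "during the first 90 days post-ablation (blanking period) may be transient in nature and not associated with the long-term effectiveness of the ablation treatment".
- Section 5.1 says that an arrhythmia with the ECG features of AF that lasts long enough "for a 12-lead ECG to be recorded, or at least 30 seconds on a rhythm strip, should be considered an AF episode".

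Section 8 promises descriptive statistics for all data and states that there are no hypotheses.

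**The concern.** The 48-hour result is a valid description of rhythm on a visit recording. The gap is that nothing else collected after the procedure is tied to it. The blanking period is named, but no outcome rule uses it. Repeat ablation is foreseen, but nothing says whether it is a failure, a censoring event or neither.

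The use suggested in section 5.2 invites a reader to take the rate as freedom from recurrence after the index ablation. A subject who was cardioverted or ablated again after blanking is not evidence that the index targets were right, yet could sit in the numerator. Section 13.2 foresees a multi-center publication and possible use in a regulatory filing, so the rate is likely to be quoted without the listings that would qualify it. Without a stated rule, two analysts could also report different AF-free rates from the same data.

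**Working it through.** The plan gives no recurrence rate, power or target to reproduce. The check has four parts.

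**1. Definition against collected data.** Take a subject whose month-12 recording is clean:

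| Other documented finding | Where it is captured | Month-12 status under 6.2.1, read literally |
|---|---|---|
| DCCV for AF after blanking | 7.3.2 | AF-free |
| Repeat ablation after blanking | 7.4; Retreatment Visit column, Tables 1 and 2 | AF-free |
| AF on the 12-lead ECG at the same visit | 7.3.2 | AF-free, although 5.1 would call it an AF episode |
| AF on the month-6 recording | 6.2.1 | AF-free at month 12 if each visit is read separately |

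The second row needs care. The repeat-ablation text in 7.4 sits in a paragraph that opens with the first 90 days. The Retreatment Visit column has no such limit, so applying the text after day 90 is an inference.

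**2. Direction on a common denominator.** Let N be the subjects with a recording at the visit, C those whose recording is clean, and k those with a clean recording and a documented post-blanking event. A positive recording at month 6 or 12 is itself a post-blanking event, because the earliest month-6 visit is about day 182 - 30 = 152.

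- 48-hour rate = C/N
- Rate counting all documented post-blanking events = (C - k)/N
- Difference = k/N, which is zero or positive

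Each such subject adds 1/100 = 1.0 point at the cap of 100 in section 6.4, or 1/50 = 2.0 points if N were 50. The documents do not give k.

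**3. Different denominators.** Hypothetical example: 100 Treatment Subjects, 90 with a month-12 recording, 18 of those showing AF, and k = 0.

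- 48-hour rate: 72/90 = 80%.
- If the other 10 have no documented event and count as free: 82/100 = 82%. The difference is -2 points.
- If the other 10 all had a documented recurrence before leaving: 72/100 = 72%. The difference is +8 points.

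So the result in step 2 does not carry over when recordings are missing.

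**4. Share of follow-up that decides the status.** I assume nominal visit days 182 and 365; the blanking period of 90 days is from section 7.4.

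- To month 6: 182 - 90 = 92 post-blanking days; 2/92 = 2.2%.
- To month 12: 365 - 90 = 275 post-blanking days; 2/275 = 0.7%.

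These are approximate minimums. The Data Collection row of the synopsis allows recordings of 48 hours or more, and both visits have a window of 30 days either way. The shares show how little of follow-up decides the status. They do not estimate k.

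**The case against.** The strongest reply is that the measure is honestly labelled. Section 6.2.1 names the instrument, and section 5.2 speaks of freedom at the two visits, not through them. The study is descriptive and unpowered, the comparison with controls is only something that may offer insight, and neither 6.2.1 nor section 8 plans it. Interim events would also appear among the data that section 8 describes.

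Most of this stands, and it limits the point to a missing measure and a missing rule. It does not remove the point. A descriptive rate still needs a defined numerator, and in a study without a test the point estimate is the main result. A list of cardioversions printed beside an AF-free rate does not say how many subjects were free of recurrence.

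A reader might go further and infer the following, which the documents do not support:

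- *The plan tells the analyst to ignore interim events.* It is silent on their role. The result in the table follows from reading the definition literally.
- *Section 5.1 already settles the 12-lead case.* It could be read as barring such a subject from AF-free status, but the background statement is not carried into 6.2.1.
- *The reported rate must overstate freedom from recurrence.* That holds only under the conditions in step 2 of the working.
- *The comparison with controls is biased in favour of the device.* The documents do not say how the controls were counted.

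A recurrence measure also has a weakness that the scheduled recording lacks: unscheduled events are detected according to each site's standard of care, across up to 15 sites. That is a reason to report both measures, not to leave one undefined.

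**Conclusion.** The point holds and should be fixed before analysis. The plan defines effectiveness only as rhythm on the visit recording. It gives no rule by which documented recurrence, DCCV, 12-lead findings or repeat ablation affect that status, and it defines no measure of freedom from recurrence after the index procedure.

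Only the direction is established, and only among the same subjects with complete recordings. The size depends on an unknown k, and the net bias against historical controls is unknown. The literal reading is firm for DCCV and for documented recurrence after blanking. For repeat ablation after day 90 it rests partly on the schedule tables.

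**What to change.** In sections 6.2.1 and 8:

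1. Keep the 48-hour result, and label it as visit-recording status, not freedom from recurrence.
2. Add, in Treatment Subjects, the proportion free from documented recurrence after the index procedure at months 6 and 12, with 95% confidence intervals, for AF and for AF/AT/AFL.
3. For analysis only, count as failure the first of these events after the 90-day blanking period: an episode longer than 30 seconds on any recording or the arrhythmia on a 12-lead ECG; DCCV for it; repeat ablation for it.
4. Use Kaplan-Meier where event dates are captured. Otherwise count events by visit interval.
5. In the visit-interval version, report subjects with no recording and no documented event as unknown, and show the result with them counted as failures and as successes. State that events near day 90 may be misclassified. The month-3 window runs from about day 76 to day 104, so 14 days are affected either way: 14/92 = 15% of the first post-blanking interval at nominal timing, and up to about 14/62 = 23% if the month-6 visit falls on day 152.
6. Report repeat ablation within 90 days, and rhythm status after repeat procedures, separately.

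The cost is wording and analysis time. No visit or monitoring is added. The documents do not say whether the Follow-Up eCRFs capture event dates, so one date field may be needed. On the same subjects the new rate will be equal to or lower than the 48-hour rate. Detection of unscheduled events will vary by site, and episodes that no recording catches will still be missed.
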